### **Dose modifications for hepatic impairment**

Ibrutinib is metabolized in the liver and therefore subjects with clinically significant hepatic impairment at the time of screening (Child-Pugh Class B or C) are excluded from study participation. For subjects who develop mild liver impairment while on study (Child-Pugh Class A), the recommended dose reduction for ibrutinib is to 140 mg daily (1 capsule). Subjects who develop moderate or severe hepatic impairment (Child-Pugh Class B or C) will have study drug withheld until resolved to mild impairment (Child-Pugh Class A) or better. Subjects who completely resolve liver impairment may re-initiate ibrutinib treatment according to Table 2. Subjects who resolve liver impairment to mild (Child-Pugh Class A) may re-start ibrutinib treatment at 140 mg daily (1 capsule). Continue to monitor subjects for signs of toxicity and follow dose modification guidance as needed (Refer to Table 2).

### **Dose modifications for planned surgery or invasive procedures**

The following recommendations should be considered during the perioperative period for subjects who require surgical intervention or an invasive procedure while receiving ibrutinib:

- a. For any planned major surgery or invasive procedure requiring sutures or staples for closure, ibrutinib should be held at least 7 days prior to the intervention and should be held at least 7 days after the procedure, and restarted at the discretion of the investigator when the surgical site is reasonably healed without serosanguineous drainage or the need for drainage tubes.
- b. For planned minor procedures (such as a central line placement, needle biopsy, thoracentesis, or paracentesis) ibrutinib should be held for at least 3 days prior to the procedure and should not be restarted for at least 3 days after the procedure. For bone marrow biopsies that are performed while the subject is on ibrutinib, it is not necessary to hold ibrutinib for these procedures.
- c. For emergency procedures, ibrutinib should be held after the procedure until the surgical site is reasonably healed, for at least 7 days after the urgent surgical procedure, or at the discretion of the investigator.

Ultimately, the management of ibrutinib in conjunction with invasive procedures depends upon the perceived bleeding risk, the subject's clinical situation, and the urgency of the procedure.

#### **6.1 Treatment Discontinuation**

Study treatment with ibrutinib will be permanently discontinued for any subject if any of the following occur.

- Grade 4 treatment related (ie, possibly-, probably-, or definitely-related) non-hematologic toxicity
- Grade 4 neutropenia lasting > 21 days
- Grade 4 thrombocytopenia lasting > 21 days or associated with clinically significant bleeding (requiring > 3 units of packed red blood cells within 24 hours)

to replace loss OR bleeding from a site which in the Investigator's opinion is a potential life-threatening source irrespective of blood loss)

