**Start of preparative regimen through Day +60 to Day +90:**

- Pre-conditioning blood sample from HCT recipient for high-throughput sequencing, flow cytometry, and CyTOF (**research**)
- Blood sample from HCT donor (related only), as a baseline to investigate development of post-transplant GVL effects (**research**)
- Disease reassessment between Day +28 and Day +60, including bone marrow examination and assessment of minimal residual disease as described above (**standard of care**)

**Prior to administration of ibrutinib (Day +60 to Day +90; all studies should be done within 2 weeks of starting ibrutinib):**

- Laboratory assessment of hepatic and renal function (**standard of care**)
- Assessment of acute GvHD presence, severity, and therapy history (**standard of care**)

- History and physical, including Karnofsky Performance Status (**standard of care**)
- Assessment of concomitant medications (**standard of care**)
- Collection of peripheral blood samples for mixed lymphocyte reactions, Th1/Th2 assays, and other correlative science endpoints (**research**)

Ibrutinib will be initiated between Day +60 and Day +90, after confirmation that the subject meets all relevant eligibility criteria. The drug will be dosed, and doses modified, as described below. The following assessments will be performed after initiation of ibrutinib:

**After start of ibrutinib until 2 years post-transplant** (tests should be performed +/- 2 weeks of given time points through Day +180, and +/- 4 weeks of given timepoints after Day +180):

- History, physical examination, and laboratory assessment of hematologic and chemistry tests per institutional standard practice (**standard of care**)
- Acute GvHD assessment weekly through Day +100 (**standard of care**)
- Chronic GvHD assessment at 6 months, 9 months, 12 months, 15 months, 18 months, and 2 years post-transplant (**standard of care**)
- Toxicity assessment at baseline (before starting ibrutinib), weekly through Day +100, monthly until Day +180, and then at 9 months, 12 months, 15 months, and 18 months post-transplant (**research**), unless ibrutinib has been permanently discontinued

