#### **4.2 Criteria for Removal from Study**

Ibrutinib will be continued until 18 months post-transplant, or until one of the following occurs: disease relapse; or discontinuation due to adverse events. Subjects with leukemia relapse after allogeneic HCT will discontinue the study drug, and may be treated with any and all appropriate therapies, including investigational agents, at the discretion of the treating physician.

Subjects will be withdrawn from study treatment if one of the following occurs: leukemia relapse; unacceptable toxicity requiring interruption of ibrutinib for more than 28 continuous days; investigator decision; withdrawal of consent by the subject for further treatment and/or follow-up; pregnancy; or study termination. All enrolled subjects, regardless of discontinuation of study treatment, will be followed for leukemia relapse and survival until 18 months after allogeneic HCT unless the subject withdraws consent for follow-up.

Withdrawal from the study will occur under the following conditions: withdrawal of consent for follow-up observation by the subject; loss to follow-up; study termination; or death. When an enrolled subject withdraws from the study, the reason for withdrawal should be documented, as should the subject's willingness to participate in follow-up visits or assessments.

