## **6. DOSE MODIFICATIONS**

The study dose levels of ibrutinib are defined as follows.

- Dose level 0: 420 mg orally once a day.
- Dose level -1: 280 mg orally once a day.
- Dose level -2: 140 mg orally once a day.
- Dose level -3: Discontinue ibrutinib.

The dose of ibrutinib should be modified according to the dose modification guidelines in Table 2 if any of the following toxicities occur and are considered to be due to ibrutinib.

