### **Non-Hematologic Adverse Events**

- Grade 3 or 4 nausea, vomiting, or diarrhea if persistent, despite optimal anti-emetic and/or anti-diarrheal therapy
- Any other Grade 4 or unmanageable Grade 3 toxicity attributed to ibrutinib

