**Table 2: Ibrutinib Dose Modifications**

Hematologic Adverse Events	
Occurrence	Action to be Taken
First	Withhold ibrutinib until recovery to an ANC $\geq$ 750 or platelets $>$ 25,000 with no evidence of Grade $\geq$ 2 bleeding; may restart at original dose level
Second	Withhold ibrutinib until recovery to an ANC $\geq$ 750 or platelets $>$ 25,000 with no evidence of Grade $\geq$ 2 bleeding; may restart at 1 dose level lower
Third	Withhold ibrutinib until recovery to an ANC $\geq$ 750 or platelets $>$ 25,000 with no evidence of Grade $\geq$ 2 bleeding; may restart at 1 dose level lower
Fourth	Discontinue ibrutinib a
Non-Hematologic Adverse Events	
First	Withhold ibrutinib until recovery to Grade $\leq$ 1 or baseline; may restart at original dose level
Second	Withhold ibrutinib until recovery to Grade $\leq$ 1 or baseline; may restart at 1 dose level lower
Third	Withhold ibrutinib until recovery to Grade $\leq$ 1 or baseline; may restart at 1 dose level lower
Fourth	Discontinue ibrutinib a

a If ibrutinib is discontinued for toxicity, subject will end the Treatment Phase of the study.

Dose changes must be recorded. At the Investigator's discretion, the dose of ibrutinib may be re-escalated after 8 weeks of a dose reduction in the absence of a recurrence of the toxicity that led to the reduction.

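### Section 6 and Table 2 allow ibrutinib to restart at the original dose after a first related Grade 4 non-hematologic toxicity; Section 6.1 requires permanent discontinuation, and no text says which governs

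*Combined protocol and SAP*

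**What the plan says.** Section 6 directs that the dose be changed according to Table 2 "if any of the following toxicities occur and are considered to be due to ibrutinib". Two non-hematologic triggers follow, and both name Grade 4. The first covers gastrointestinal events: "Grade 3 or 4 nausea, vomiting, or diarrhea if persistent, despite optimal anti-emetic and/or anti-diarrheal therapy". The second is a general category for everything else of that kind: "Any other Grade 4 or unmanageable Grade 3 toxicity attributed to ibrutinib".

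For a first non-hematologic occurrence, Table 2 has ibrutinib held until recovery to Grade 1 or less "or baseline; may restart at original dose level". The second and third occurrences allow a restart one dose level lower. Discontinuation comes at the fourth. No row makes an exception for Grade 4.

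Section 6.1 then says: "Study treatment with ibrutinib will be permanently discontinued for any subject if any of the following occur". The first condition on its list is "Grade 4 treatment related (ie, possibly-, probably-, or definitely-related) non-hematologic toxicity", with no count of occurrences and no requirement that the event persist.

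**The concern.** The two rules give different instructions for the same event. An investigator working from Table 2 could rechallenge at full dose after a Grade 4 drug-related event that Section 6.1 says must end treatment, while an investigator at another site stops the drug for good. Section 12.4 plans three centers, so divergent handling is a realistic prospect. The subjects are recent allogeneic transplant recipients, and the protocol itself reports fatal bleeding (Section 4.1) and fatal infections (Section 5.1) with this drug.

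There is a secondary effect on safety data. Under Section 4, scheduled toxicity assessment continues through 18 months post-transplant "unless ibrutinib has been permanently discontinued", so the length of that schedule for an affected subject depends on which rule the site applied.

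**Working it through.** The plan states no figure to reproduce on this point. The check sets the two rules side by side and counts the restarts that each allows.

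**1. Do the rules cover the same events?** Section 6 uses attribution to ibrutinib; Section 6.1 uses possible, probable or definite relatedness. An event attributed to the drug is at least possibly related, so every Grade 4 non-hematologic event that Section 6 sends to Table 2 also meets Section 6.1. No such event can use Table 2's restart step without breaching Section 6.1.

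**2. What does each rule allow?** Dose levels are from Section 6: level 0 = 420 mg, level -1 = 280 mg, level -2 = 140 mg, level -3 = discontinue. Each reduction in Table 2 is read as one level below the dose then in use.

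| Related Grade 4 non-hematologic event, subject on 420 mg | Section 6 / Table 2 | Section 6.1 |
|---|---|---|
| 1st | hold, may restart at 420 mg | discontinue permanently |
| 2nd | hold, may restart at 280 mg | not reached |
| 3rd | hold, may restart at 140 mg | not reached |
| 4th | discontinue | not reached |

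Restarts permitted after one event: 1 against 0. Maximum over repeated events: 1 + 1 + 1 = 3 against 0. For a subject treated as being at level -2, the second occurrence would already lead to level -3, so the maximum is 1 against 0.

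**3. Does any other text settle the order?**

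- The Table 2 footnote says only that a subject who discontinues for toxicity ends the Treatment Phase.
- Section 4.2 adds a separate criterion, toxicity that interrupts ibrutinib for more than 28 continuous days, and does not rank the other two rules.
- The Section 5.1 risk paragraphs on atrial fibrillation, diarrhea and interstitial lung disease refer the reader to the dose modification guidelines in Section 6 and do not mention the discontinuation rule.

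**4. Is the rest of Section 6.1 compatible with Table 2?** Yes. The hematologic conditions in Section 6.1 add something that separates a stop from a restart: Grade 4 neutropenia lasting more than 21 days, or Grade 4 thrombocytopenia lasting more than 21 days or with clinically significant bleeding. The non-hematologic condition adds nothing of that kind, so the conflict is confined to Grade 4 non-hematologic events. The Grade 3 path through Table 2 is unaffected.

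**5. Does it reach the primary analysis?** No. Section 4.2 says that all enrolled subjects, "regardless of discontinuation of study treatment, will be followed for leukemia relapse and survival until 18 months after allogeneic HCT", unless they withdraw consent for follow-up. Section 12.3 defines the populations by enrollment and by receipt of at least one dose, and neither depends on a restart.

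**The case against.** The strongest reply is that the wording already ranks the rules. Table 2 is called a guideline and says only that the drug may restart; Section 6.1 is mandatory and applies to any subject. A permission does not cancel a mandatory stop, and a site that holds the drug and never restarts it complies with both. The hematologic conditions, where Section 6.1 plainly sits on top of Table 2, support the same reading. This is the safer reading and probably the one intended. But it is an inference that the protocol does not state, and it leaves the explicit Grade 4 restart path in Section 6 with no effect.

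A second reply is that the three-restart figure overstates the matter. It needs four separate related Grade 4 events in one subject on 420 mg, all handled under Table 2, each recovering within the 28-day limit of Section 4.2. Section 6 also expects most subjects to be on azoles until at least Day +75, with ibrutinib at 140 mg meanwhile. This is fair: three is a ceiling under stated conditions, and the core contrast is one restart against none.

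Third, the toxicity-assessment effect is small. Section 7.2 has subjects evaluated for adverse events at every clinic visit, and unresolved serious events are followed further. That stands, which is why the point is secondary.

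**Conclusion.** The concern holds. For a first Grade 4 non-hematologic toxicity attributed to ibrutinib, Section 6 with Table 2 permits a restart at the original dose and Section 6.1 forbids any restart, with no rule of precedence. The size is one permitted restart against none per event, with a ceiling of three against none for a subject on 420 mg with repeated events and stepwise reductions. How many subjects this would touch cannot be stated, because the documents give no expected rate of related Grade 4 non-hematologic events. It should be fixed as a matter of subject safety and uniform conduct; it does not threaten the primary analysis.

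**What to change.** Delete Grade 4 from the two non-hematologic triggers in Section 6, leaving persistent Grade 3 nausea, vomiting or diarrhea and other unmanageable Grade 3 toxicity. Table 2's non-hematologic rows then cover Grade 3 events only. Add one sentence stating that Section 6.1 takes precedence over all restart provisions in Section 6. That wording is better than naming Table 2 alone, because the hepatic-impairment paragraph in Section 6 also allows a direct restart at 140 mg. For Grade 4 events, keep Section 6.1's relatedness threshold of possibly, probably or definitely related. If the sponsor's clinical team wants rechallenge after particular Grade 4 events, name them as exceptions in Section 6.1.

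The cost is a protocol clarification: two trigger lines edited and one sentence added, with no extra subjects, visits or analyses.

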## 7. ADVERSE EVENTS AND REPORTING PROCEDURES

### 7.1 Potential Adverse Events

Please see "Risks" in Section 5.1 above for a full description of known risks and toxicities associated with ibrutinib.

### 7.2 Adverse Event Reporting

Adverse events will be graded according to CTCAE v4.03. Both Serious and Non-Serious Adverse Events will be clearly noted in source documentation and listed on study specific Case Report Forms (CRFs). The Protocol Director (PD) or designee will assess each Adverse Event (AE) to determine whether it is unexpected according to the Informed Consent, Protocol Document, or Investigator's Brochure, and related to the investigation. All Serious Adverse Events (SAEs) will be tracked until resolution, or until 30 days after the last dose of the study treatment.

An adverse event (AE) will be defined as any medical change in the subject's baseline or pre-treatment condition (occurring during the course of the clinical study) after receiving the study drug (ibrutinib), whether considered treatment-related or not.

Adverse events will be monitored spontaneously by the subject or will be discovered as a result of general questioning by the investigator or by physical examination. All adverse events will be recorded. As far as possible, each adverse event will be described by its duration (start and end dates), frequency (single episode, intermittent, continuous), severity (mild, moderate, severe) and assessment of its cause (the underlying study indication, co-existing disease, concomitant medication, investigational drug, or other), relationship to investigational drug (unrelated, unlikely, possibly, probably, definitely), whether it influenced the course of treatment, whether it required specific therapy and what is expected or unexpected. All adverse events will be graded on a three point scale of increasing severity. Serious adverse events will be reported to the IRB and appropriate regulatory agencies.

An adverse event is any significant medical occurrence in a subject treated on this protocol both during treatment and follow-up period, regardless of causality assessment. This includes adverse clinical or laboratory findings, inter-current illness, or an exacerbation or progression of a condition present at the time of study initiation. An adverse event is considered serious if it fulfills one of the following criteria:

- a. Results in death
- b. Life-threatening (subject at risk of death at the time of the event)
- c. Requires inpatient hospitalization or prolongation of existing hospitalization
- d. Results in persistent or significant disability
- e. Other medical events that may not be immediately life-threatening or result in death or hospitalization but may jeopardize the subject or require intervention to prevent one of the outcomes listed above

Study subjects will be instructed to report any adverse events to investigators and subjects will be evaluated for adverse events at every clinic visit. All adverse events will be documented by investigators and will contain the following information, if known:

- a. Medical diagnosis of the event
- b. Date and time of onset of event
- c. Date and time of resolution of event
- d. Severity of the event according to the National Cancer Institute (NCI) Common Toxicity Criteria and Adverse Events (CTCAE) criteria, version 4.0
- e. Frequency of the event
- f. Intervention
- g. Outcome
- h. Likelihood of association between the event and the study drug

The following are NOT considered AEs:

- **Pre-existing condition:** A pre-existing condition (documented on the medical history CRF) is not considered an AE unless the severity, frequency, or character of the event worsens during the study period.
- **Pre-planned or elective hospitalization:** A hospitalization planned before signing the informed consent form is not considered an SAE, but rather a therapeutic intervention. However, if during the pre-planned hospitalization an event occurs, which prolongs the hospitalization or meets any other SAE criteria, the event will be considered an SAE. Surgeries or interventions that were under consideration, but not performed before enrollment in the study, will not be considered serious if they are performed after enrollment in the study for a condition that has not changed from its baseline level. Elective hospitalizations for social reasons, solely for the administration of chemotherapy, or due to long travel distances are also not SAEs.
- **Diagnostic Testing and Procedures:** Testing and procedures should not to be reported as AEs or SAEs, but rather the cause for the test or procedure should be reported.

Serious adverse events (SAEs) CTCAE Grade 3 and above, and all subsequent follow-up reports will be reported to the Stanford Cancer Center Data and Safety Monitoring Committee (DSMC) using the study specific CRF regardless of the event's relatedness to the investigation. Following review by the DSMC, events meeting the IRB definition of 'Unanticipated Problem' will be reported to the IRB using eProtocol within 10 working days of DSMC review, or within 5 working days for deaths or life-threatening experiences. If complete information is not available at the time, the investigator must provide follow-up information as soon as it is known.

Adverse events that are serious and unexpected suspected adverse reactions, and are possibly, probably, or definitely related to the study drug ibrutinib (SUSAR per 21CFR§312.32), will be reported to the FDA via IND Safety Report [21CFR§312.32]

within 14 calendar days, or within 7 calendar days if the event is an unexpected fatal or life-threatening suspected adverse reaction.

In addition, all serious adverse events (initial and follow-up information) will be reported on the Serious Adverse Event Report Form from Pharmacyclics and sent via email or fax to Pharmacyclics Drug Safety or designee within 24 hours of the discovery of the event or information. Pharmacyclics may request follow-up and other additional information from the Investigator (for instance, hospital admission/discharge notes and laboratory results). The contact information (phone, email and fax) for Pharmacyclics Drug Safety can be found on the Serious Adverse Event Report Form and instructions.

Hematopoietic cell transplantation (HCT) is an aggressive therapy for the treatment of a number of life-threatening malignant and non-malignant disorders. Individuals considered for HCT have generally exhausted other avenues of effective therapy. The non-relapse mortality (NRM) associated with a sibling-donor myeloablative allogeneic transplant is approximately 20% and the NRM for an unrelated-donor myeloablative allogeneic transplant ranges from 20-50%. In the setting of reduced-intensity conditioning and allogeneic HCT, the NRM is approximately 10% with a sibling donor and 20% with an unrelated donor.

As an aggressive therapy, HCT is associated with a large number of AEs and SAEs. The toxicities associated with HCT are related to the following: 1) the underlying disease; 2) therapy antecedent to HCT; 3) the health status of the transplant recipient, including co-existing conditions; 4) the preparative regimen employed before transplant; 5) therapies directed at reducing transplant-related complications (eg, immunosuppressants for the prevention of GvHD); and 6) the treatment of complications of HCT.

The use of toxicity grading scales such as the NCI CTC is a standard in the medical community for the reporting of AEs and SAEs in the investigation of new drugs or devices. The use of this type of scale is less helpful in the evaluation of AEs and SAEs associated with a treatment, such as HCT. In an effort to report to regulatory agencies the toxicities that are relevant and meaningful for the evaluation of risks and benefits to potential HCT recipients, the following guidelines will serve to determine which events are reported as AEs and SAEs.

The following SAEs require reporting to the Stanford Cancer Institute Data Safety Monitoring Board for subjects on research protocols. If the event is unexpected, serious, and harmful, then it will also require reporting to the IRB:

